Stage 2 (months 2-5): The focus of stage 2 is on behavioural and interactional change within the young person and their parents in their relationships, as well as their extrafamilial areas. MDFT helps the young person improve self-awareness, self-worth, and confidence, while developing short and long-term goals, improving emotional regulation, coping, problem solving and communication skills. The focus for parents is on strengthening parental teamwork, improving parenting skills and practices, rebuilding parent-child emotional bonds and enhancing parents' individual functioning. In the family domain, MDFT improves family communication, problem solving skills, strengthens emotional attachments between family members and improves everyday family functioning. In the community, the focus is on improving the family's relationships with social systems including, school, the workplace and their wider community while building capacity to access support when needed. If court-involved, the MDFT team is active in helping young people comply with terms of court orders and reducing recidivism.

Stage 3 (month 6): In the last month of the programme therapists highlight the achievements and support families to create action plans for responding to family arguments, substance use relapse or other potential setbacks. Family members engage in self-reflection, acknowledging the efforts made by each other and expressing hope for the future. It is the young person and their family's launch into the next chapter of their lives.

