Consent and baseline assessment will be conducted by staff employed by Barnardo's they will be conducted in a safe, therapeutic and convenient location for the young person, this will include facilities managed by Barnardo's, community facilities accessed as part of community partnerships, children's services, school and the young person's home. Data will be collected on-line, and randomisation will be conducted independent of Barnardo's by research staff after baseline data collection has been conducted.

Inclusion criteria

- 1. Young people aged 13-17 years inclusive who are resident in the Bristol or Newport LA.
- 2. Currently involved with the police or youth justice service or at risk of offending.

At risk of offending defined as having at least one of the following risk factors, assessed on referral.

- Previously being in the secure estate.
- Currently, or previously, persistently absent from school (defined by DfE as 10% or more).
- Have been the victim of violence.
- Currently, or have attended alternative education provision.
- Received multiple suspensions from school or has been permanently excluded.
- Have a sibling or parent who has been involved in serious violence or identified as facing exploitation harm.
- Currently, or have been, in the care system.
- Have been identified as being at risk of criminal exploitation.
- Currently or have had a social worker.
- Have previously been in contact with youth justice services.
- Have been arrested, admitted an offence and released by the police with no further action.
- 3. Evidence of alcohol or substance use on at least 4 occasions in the past 28 days, assessed using a single substance use frequency question on referral to Barnardo's.
- 4. Willing and able to provide informed consent or willing to provide assent with a parent/ carer willing to provide consent.

Exclusion criteria:

- 1. Alcohol or substance severity that requires inpatient residential treatment or immediate detoxification.
- 2. Severe mental health condition requiring immediate psychiatric assessment.

Figure 3: Flow chart of recruitment processes.

Referral partners identify young people who would be suitable for MDFT

Referral partners share information with Barnardo's through secure referral form.

Barnardo's contacts young person to assess frequency of substance use, check eligibility, and gauge interest, share information sheet and privacy notice

If willing to take part young person attends for baseline assessment

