In adolescent populations a standard TLFB with a recall period of 28 days. Frequency of use is calculated as percent days abstinent from alcohol and/ or other substances in the previous 28-days. It provides a fractional outcome and is far more detailed than standard measures of alcohol and substance use and can yield information on the overall frequency of alcohol and substance use, frequency of individual substances, quantity of use and periods of heavy episodic use. With a trained researcher the TLFB28 takes on average 10 minutes to complete.

The covariate for the primary outcome is assessed at eligibility and baseline using a Single Substance Use Question (SSUQ; (Levy et al., 2021)) over the past 28-days. This single frequency question reduces the burden on participants at baseline and addresses the issue of potential assessment reactivity, where the assessment of substance use in detail acts as a brief intervention. The SSUQ meets the criterion as a covariate for adolescent populations in that it is highly correlated with frequency of substance use derived from the primary outcome time line follow-back 28 (rho = 0.903 for alcohol and 0.830 for drugs).

Secondary outcomes

Self-reported violent offending will be assessed using the volume score of the Self-Report Delinquency Scale (SRDS; (Smith and McVie, 2003)) over the previous six months. This 19-item questionnaire has established psychometric properties (Fonagy et al., 2018) in this population and has a strong correlation (R=0.95) with police charges (McAra and McVie, 2007). Violent offences are classified as carrying a weapon, robbery, assault, racial assault and fire setting.

Emotional symptoms and behavioural difficulties will be assessed using the self-completed Strength and Difficulties questionnaire (SDQ; (Goodman, 1997)). This assesses behaviour across several domains including, conduct, hyperactivity, emotional regulation, peer relationships and prosocial behaviour and allows for the generation of two multi-component outcomes: internalising and externalising behaviours with the latter highly associated with current or future offending behaviour. We will assess total score, externalising behaviour, internalising behaviour. The outcome is widely used and has demonstrated excellent validity and moderate reliability in adolescent populations (Goodman, 2001). The SDQ is suitable for

completion by those aged 10-17 years and those with mild learning disabilities (Law and Wolpert, 2014).

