e) Performed poorly at school or work		⊢		⊢		 	
f) Victimized by robbery or theft		⊢	∐		.	 	 
g) Trouble with police	⊢	⊢	⊢		 	⊢	-
h) Hospitalised or admitted to an emergency room	⊢		⊢		 	·	-
i) Engaged in sexual intercourse without a condom	⊢	⊢	⊢	⊢	H	H	-님
j) Engaged in sexual intercourse you regretted the next day							🔲
	1	2	3	4	5	6	7

Motivation – Readiness Ruler

Single item readiness ruler

On the scale below enter how you feel right now about your substance use

1 2 3 4 5 6 7 8 9 10

I never think about my substance use Sometimes I think about using substances less often

I have decided to use substances less often I am already trying to use fewer substances My substance use has changed I use less than before

Family Relationships - Brief Family Relationship Scale

Responses True or False

Cohesion

- 1. In our family we really help and support each other.
- 2. In our family we spend a lot of time doing things together at home.
- 3. In our family we work hard at what we do in our home.
- 4. In our family there is a feeling of togetherness.
- 5. My family members really support each other.
- 6. I am proud to be a part of our family.
- 7. In our family we really get along well with each other.

Expressiveness

- 8. In our family we can talk openly in our home.
- 9. In our family we sometimes tell each other about our personal problems.
- 10. In our family we begin discussions easily.

Conflict

- 11. In our family we argue a lot. (R)
- 12. In our family we are really mad at each other a lot. (R)
- 13. In our family we lose our tempers a lot. (R)
- 14. In our family we often put down each other. (R)
- 15. My family members sometimes are violent. (R)
- 16. In our family we raise our voice when we are mad. (R)

Time Line Follow-Back - TLFB28 - completed using interview rather than self-complete

To help us evaluate your drug use, we need to get an idea of what your use was like in the past _____ days. To do this, we would like you to fill out the attached calendar.

- ✓ Filling out the calendar is not hard!
- √ Try to be as accurate as possible.
- ✓ We recognize you won't have perfect recall. That's OKAY.

✓ WHAT TO FILL IN

- The idea is that for each day on the calendar we want you to indicate whether you "used" or "did not use" drugs.
- On days when you did not use drugs, you should write a "0" in the box.
- On days when you did use drugs, you should put a "√" in the box.

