It's important that something is written for every day, even if it is a "0".

√ YOUR BEST ESTIMATE

- . We realize it isn't easy to recall things with 100% accuracy.
- If you are not sure whether you used a certain drug on a Thursday or a Friday of a certain week, give it
 your best guess! The goal is to get a picture of how many days you were using drugs and your patterns
 of use.

√ HELPFUL HINTS

- Holidays such as Thanksgiving and Christmas are marked on the calendar to help you better recall your
 use. Also, think about whether you used drugs on personal holidays and events such as birthdays,
 vacations, or parties.
- If you have regular drug use patterns you can use these to help you recall your use. For example, you
 may have weekend/weekday changes in your drug use or your drug use may be different depending
 where you are or whom you are with.

✓ COMPLETING THE CALENDAR

- A blank calendar is attached. Each day should contain a "0" for no drug use or a "√" for drug use.
 The time period we are talking about on the calendar is
- from ________to ______
- . In estimating your drug use, be as accurate as possible.
- DOUBLE CHECK THAT ALL DAYS ARE FILLED IN BEFORE RETURNING THE CALENDAR.
- Before you start look at the SAMPLE CALENDAR on the next page.

✓ SAMPLE CALENDAR

2000	SUN	MON	TUES	WED	THURS	FRI	SAT
							2
						0	0
S	3	4 Labor Day	5	6	7	8	9
	0	0	✓	✓	✓	0	✓
Е	10	11	12	13	14	15	16
	✓	✓	0	✓	√	0	✓
Р	17	18	19	20	21	22	23
	✓	0	0	0	0	✓	✓
_	24	25	26	27	28	29	30
Т	0	0	✓	0	0	0	✓

Substance Use Screening Questionnaire – SUSQ

"On how many days in the past 28 days have you used alcohol or other illegal substance (list prompt)?"

youthendowmentfund.org.uk

[contact]

@YouthEndowFund

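### The 28-day calendar has no code for days in custody, hospital or residential treatment, so non-use days there count as abstinent and no described instrument separates them by arm

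*Protocol*

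**What the plan says.** **Outcome.** The Primary outcome section of the protocol states: "Frequency of use is calculated as percent days abstinent from alcohol and/ or other substances in the previous 28-days". The denominator is 28 days, and no class of day is set apart. The month 12 secondary outcome uses the same measure.

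**Form.** The TLFB28 sheet in Appendix IV says "for each day on the calendar we want you to indicate whether you" used drugs or did not. For non-use, "On days when you did not use drugs, you should write a" zero; for use, "On days when you did use drugs, you should put a" tick. Blanks are not allowed: "It's important that something is written for every day, even if it is a" zero.

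**Population.** Participants must be "Currently involved with the police or youth justice service or at risk of offending". The Participants section expects 30% of referrals to be involved with the criminal justice system at the time. The exclusion for "Alcohol or substance severity that requires inpatient residential treatment or immediate detoxification" applies at entry. Nothing is said about admission or detention after randomisation.

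**Intervention.** Under Stage 2, for court-involved cases, the "MDFT team is active in helping young people comply with terms of court orders and reducing recidivism".

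**Other instruments.** Table 1 gives the CSRI content as arrests, cautions, charges, court attendance, suspensions, exclusions, managed moves and employment status. The recall period is six months.

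**The concern.** A young person who is detained or admitted has little or no access to alcohol or drugs. The calendar as shown gives that day the same mark as a day of abstinence at home. If such days are equally common in both arms, they do little to the comparison. If they differ, part of the observed difference in abstinence reflects confinement and not a change in behaviour.

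An imbalance is plausible here because the intervention works on court orders and reoffending, and because it would arise after randomisation. If MDFT succeeds on that front, BAU would have more controlled days and so more days marked as non-use, which would narrow the apparent benefit of MDFT.

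An analysis plan could set a rule for these days, but it could apply the rule only if the days had been recorded. The point therefore belongs to the data collection fixed in the protocol.

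**Working it through.** **1. Can any described instrument identify the days?**

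- TLFB28 calendar (Appendix IV): two marks, every day filled. A non-use day in custody or hospital can only be a zero.
- CSRI (Table 1, Secondary outcomes, Table 4): eight topics are named and Table 4 counts eight items, over six months. None of the named topics is days held or admitted. The form itself is not reproduced, and Appendix I adds school attendance, so the list may not be complete.
- ESPAD problem items (Appendix IV): one item on hospital or emergency admission, limited to alcohol-related occasions, in bands, over 12 months. It cannot be placed in a 28-day window.

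No dated record of controlled days is described.

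**2. One participant (hypothetical).** Fourteen controlled days without use, then use on 7 of 14 days at liberty:

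- as scored: (14 + 7)/28 = 75% abstinent;
- over days at liberty: 7/14 = 50%.

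**3. Scale of the planned effect.** The protocol gives no figure on controlled days. Its sample size gives the yardstick: effect size 0.27, power 80%, two-sided alpha 0.05, correlation 0.4.

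- Per arm: 2 × (1.960 + 0.842)² × (1 − 0.4²)/0.27² = 2 × 7.85 × 0.84/0.0729 = 180.9, so 181, or 362 in total. The t-based calculation gives 364, the stated number.
- The SD of percent days abstinent is not given. Assuming 30, 40 or 48 points, 0.27 SD is 8.1, 10.8 or 13.0 points. The 48 is what the protocol's 13% difference would imply if it is absolute: 13/0.27 = 48.

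**4. Shift in the difference between arms.** Let c be the share of all outcome days in an arm that are controlled, and p the proportion of days abstinent at liberty. Assume no use on controlled days and the same p in both arms.

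- Scored abstinence = c + (1 − c)p = p + c(1 − p).
- Difference (BAU − MDFT) = (c for BAU − c for MDFT) × (1 − p).

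Both the gap and p are assumptions:

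| Gap in share of controlled days | p = 70% | p = 50% | p = 30% |
|---|---|---|---|
| 1 point | 0.3 | 0.5 | 0.7 |
| 2 points | 0.6 | 1.0 | 1.4 |
| 5 points | 1.5 | 2.5 | 3.5 |

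Entries are percentage points of abstinence added to the arm with more controlled days. At a 1-point gap and p = 50%, 0.5 points is 6%, 5% or 4% of the planned effect for SD 30, 40 or 48.

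For a sense of the gaps: with 182 analysed per arm, 1 point equals about 1.8 participants held for the whole window (0.01 × 182), and 5 points about 9.1 (0.05 × 182).

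**The case against.** The case against has several parts, and much of it stands.

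- **The form is a generic template.** It has a blank for the number of days, a sample calendar from 2000 with US holidays, and refers only to drugs. The Primary outcome section says the trial's instrument also yields quantity and individual substances, which this sheet cannot. The interview may record more than is shown. That stands: scoring controlled days as abstinent is an inference from the form, not a statement in the protocol. It is still the only calendar shown, and nothing in the text adds a code.
- **A reader might infer that controlled days can never be identified.** The documents do not go that far. The CSRI form is not reproduced, and adverse-event reports or the pilot's monitoring of BAU services might hold something, though neither is described as giving dated days. The supportable statement is that no such record is described.
- **A reader might call the primary comparison biased.** The primary research question concerns the frequency of self-reported use, and the analysis is by intention to treat. A day in custody without use is truly a day without use, so this is a matter of interpretation and the primary outcome need not change.
- **A reader might expect residential placement by MDFT therapists to favour MDFT.** Nothing in the documents supports that route.
- **A reader might say that the worst courses score as the best outcomes.** That holds only where confinement fills the whole window.
- **Numbers may be small.** About 70% of referrals are expected not to be in the justice system, and being in it is not custody. Follow-up is by video link, so some detained participants may be missing and not scored at all. This stands as to size, but a participant released within the window would still be affected.

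**Conclusion.** The gap is real and limited. On the calendar as shown, non-use days in a controlled environment count as abstinent, and no described instrument records them within the 28 days. The population and the aims of MDFT make a difference between arms plausible, most likely flattering BAU, but the documents do not establish that one will occur.

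The size is unknown. The protocol gives no custody or inpatient rates, no SD and no expected abstinence at liberty. The one usable rule is conditional: at an assumed 50% abstinence at liberty, each 1-point gap in the share of controlled days moves the difference by about 0.5 points (0.3 to 0.7 for abstinence of 70% to 30%). The larger gaps in the table show how the shift scales and are not forecasts. A reader might conclude that a substantial part of the planned effect is masked; that would rest wholly on assumed rates. The point is worth acting on because the remedy is cheap and days not recorded at interview may not be recoverable.

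**What to change.** - Keep the primary outcome as defined.
- Add one code to the TLFB28 calendar at months 6 and 12 for days in a controlled environment (custody, secure accommodation, hospital or residential treatment), recorded alongside use or non-use.
- Report these days by arm.
- Pre-specify one supportive sensitivity analysis of percent days abstinent over days not in a controlled environment. State that it conditions on a post-randomisation event, so it supports interpretation and does not replace the primary analysis.

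A matching baseline item is optional. Entry requires use on at least 4 occasions in the past 28 days, which largely rules out confinement for the whole baseline window.

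The cost is about a minute in an interview already led by a researcher, and one extra analysis.

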The proposed research aims to address key questions about the efficacy of MDFT, adapted for use within the UK using a mixed method, two-arm, prospective, individually randomised controlled trial comparing MDFT versus business as usual (BAU). The trial will have an embedded internal pilot to address key questions regarding the parameters for a definitive efficacy study and a concurrent implementation and process evaluation addressing important questions regarding the MDFT intervention in detail.

Intervention

Delivery of MDFT will occur between July 2025 and July 2027. MDFT aims to reduce substance use, improve behavioural issues and reduce young people's involvement in the criminal justice system through multidimensional family therapy. Greater detail on the theoretical framework is available here https://www.mdft.org and a theory of change diagram and narrative provided in figure 2 and appendix I. It is delivered by a qualified MDFT therapist, and it intervenes in four connected areas: (i) the young person, (ii) the parents, (iii) the family, and (iv) the community. The main activities that drive behavioural change are (i) individual therapy sessions between the therapist and young person (typically 8-20 individual sessions), (ii) parent sessions between the therapist and parents (typically 4-10 sessions), (iii) family sessions where the therapist facilitates meaningful conversations among the family members who attend (typically 4-10 sessions), and (iv) sessions between the family and social systems in their community (typically 4-10 community sessions/meetings). Additional activities outside of the session promote individual change, and phone calls to the young person and parents support the development of problem-solving skills for when difficulties in relationships arise.

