Compliance

We will assess adherence using the MDFT clinical portal, this assesses the dose and duration of interventions planned and delivered including the specific domains targeted at each session. A minimum dose of MDFT is defined as completion of the following metrics over a 6-month period.:

- Adolescent-only Sessions: 55% of total sessions being completed.
- Family Sessions: 30% of total sessions (includes the time within family sessions when therapist might have a little one on one time with youth or parent if needed).
- Parent/ carer-only sessions: 15% of total sessions (maybe with a single parent/ carer alone, and/ or time with the parenting team/ system together.

We plan on conducting a secondary analysis using a Complier Average Causal Effects (CACE) model using an instrumental variable framework. CACE analysis allows us to avoid bias by weighting the ITT treatment effect by compliance with the intervention or control treatment received, this provides an unbiased estimate of the role of compliance in the outcomes observed. By using different thresholds of compliance, a minimum threshold of 12 sessions over 4 months versus complete compliance, we can explore the nature of the relationship between compliance with the intervention and outcomes observed.

Analysis

Pilot study analysis

In the pilot study we will explore the distributional assumptions for each outcome measure and present descriptive statistics, either parametric or non-parametric overall, by allocated group and by stratification variables. We will estimate likely proportions of participants who are eligible, consent and followed up at 6 months. Each of these will be assessed against progression criteria detailed in appendix I (**PRQ1**, **PRQ2**).

We will conduct a descriptive analysis of outcomes including measures of central tendency and estimates of precision for continuous outcomes and proportions for categorical outcomes. Inferential analysis at the pilot stage will focus on the primary outcome and will involve a futility analysis using a fractional regression adjusted for stratification variables. This will allow us to confirm or revise our sample size calculation (**PRQ3, PRQ4**).

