Therapists need access to safe, supportive and therapeutic spaces within the community in which they can build relationships with children and families. Barnardo's has access to community buildings through partnerships with the Local Authorities, VCSE networks and youth work providers across Newport and Bristol. Local management are embedded within both Newport and Bristol, and are fully cognisant of local factors including geography, demography, need and support services, allowing us to target and understand the background and support needs of children and families, and access resources as required.

In Bristol, Barnardo's own a building at Old Market (Bristol Centre), which is located for ease of access to children and families. It has been decorated in co-production with young people who use it to be welcoming, therapeutic and trauma-informed throughout, and contains dedicated safe spaces for therapeutic delivery.

The MDFT team in each site usually consists of 6-8 therapists, one who is trained to act in a supervisory role. Training in MDFT is provided by MDFT international who provide an intensive training package and full certification. Training includes the assessment of the needs of children and families and case formulation to meet those needs. All therapists have access to supervisory support from the site based MDFT supervisor and the wider MDFT international team. MDFT therapists have access to the MDFT portal to record planned and delivered sessions.

Activities

The specification with respect to number of adolescent alone session, parent sessions without their adolescent, family sessions are guidelines are not dictates or requirements. The exact configuration is very individualised to the need of the young person and family. MDFT is not a curriculum-based intervention but instead is a psychotherapy where the exact interventions applied, types of sessions, weekly dose, length of treatment episode is determined by the needs of the young person and family. A minimum dosage is considered 12 sessions over a 4-month period.

MDFT typically consists of 2 sessions per week lasting anywhere from 45 to 90 minutes. 90 minutes may be necessary for multipart family sessions. Individual sessions alone with the young person typically range from 45 – 60 minutes, sessions alone with the parents are usually 60 minutes.

Mechanisms

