Appendix II: Progression criteria from internal pilot

Project implementation

Area	Question	Assessment	Criteria	Rag rating
Therapist Recruitment	Have sufficient therapists been	Number of therapists recruited	7	>6 in post
	recruited			<6 >4 in post
				<4 in post
Therapist Training	Have sufficient therapists been	% of therapists certified	75%	>75%
	certified			60 – 74%
				<60%
Therapist Supervision	Do therapists attend planned supervision	% of therapist supervision sessions attended	75%	>75%
				60 – 74%
				<60%
Therapist Capacity	ls there sufficient capacity to provide MDFT Is there sufficient capacity to provide capacity Model of randomisation/ capacity		100%	100%
			90-99% increase number of therapists by 1	
				<90% increase number of therapists by required number
			80%	>80%

Dosage within 4-6 months 55% adolescent sessions 30% family sessions 15% parent alone sessions	Do participants comply with the minimal dose of MDFT	% participants receiving minimal dose		60-79% <60%
Eligible referrals	Are sufficient referrals eligible	% of eligible participants who consent	80%	>80% 50 - 79% <50%
Acceptability of adaptions	Are the adaptions to MDFT acceptable to therapists and participants	Review of adaptions	Adaption should be acceptable	Acceptable to some but not all revise adaption Not acceptable

Internal pilot evaluation

Area	Question	Assessment	Criteria	Rag rating
Participant recruitment	· ·	60	60	
				42-60
				<42
Evaluation attrition	aluation attrition Have sufficient % of participan participants been retained		90%	>90%
				70 – 89%

	retained at 6- months			<70%
Proportion with primary outcome	Have sufficient participants	% of participants completing primary	95%	>94%
recorded at month	provided a primary outcome	outcome		75 – 94%
				<75%%
Proportion with secondary outcome	Have sufficient participants	% of participants completing	80%	>80%
recorded at month 6	provided a secondary	secondary outcome		60 – 79%
	outcome			<60%
Analysable primary and secondary	secondary participants who providing usefull	providing usefull primary and secondary	80%	>80%
outcome data				60 – 79%
		outcomes		<60%
Randomisation	Are the groups allocated to MSFT and BAU of similar size	Difference in the proportion allocated to each group	2%	<2%
				3-5%
				>5%
Randomisation	Are the groups allocated to MSFT	Difference in the proportion allocated to each group by	5%	<5%
	and BAU of similar size by stratification			5-10%
stratific		stratification		>10%

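### The pilot's minimum-dose criterion is a session mix adding to 100% with no amount of therapy, and it conflicts with the protocol's own minimum of 12 sessions over 4 months

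*Protocol*

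**What the plan says.** The Protocol states a minimum dose in four places.

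- **Compliance, definition.** "A minimum dose of MDFT is defined as completion of the following metrics over a 6-month period". The metrics are "Adolescent-only Sessions: 55% of total sessions being completed", 30% of total sessions for family work and 15% for parent or carer sessions. No session count is given.
- **Compliance, CACE paragraph.** The lower compliance level is "a minimum threshold of 12 sessions over 4 months versus complete compliance".
- **Appendix I, Activities.** "A minimum dosage is considered 12 sessions over a 4-month period". The same paragraph describes the mix differently: the numbers of adolescent, parent and "family sessions are guidelines are not dictates or requirements".
- **Appendix II, progression criteria.** The item asks "Do participants comply with the minimal dose of MDFT" and describes the dose as "Dosage within 4-6 months 55% adolescent sessions 30% family sessions 15% parent alone sessions". It is scored as the percentage of participants receiving the minimal dose: green above 80%, amber 60-79%, red below 60%.

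The Intervention section gives typical counts: "individual therapy sessions between the therapist and young person (typically 8-20 individual sessions"), with 4-10 each for parent, family and community sessions.

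**The concern.** A minimum dose should say how much therapy is enough. Shares of a total say only how the sessions were divided, whatever the total was. The definition in Compliance and the Appendix II item have no session count, no tolerance around the shares, and no statement of whether community sessions count in the total.

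The same protocol gives a count-based minimum twice, does not link it to the shares, and says in Appendix I that the session mix is not a requirement. The time window also varies: 6 months in the Compliance definition, 4-6 months in Appendix II and 4 months in the count rule.

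At stake is one red/amber/green item in the pilot's transition decision. If the rule can be read in several ways, its rating can be settled after the delivery data are seen. A pass on mix could also hide under-delivery.

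**Working it through.** The protocol gives no figure to reproduce here, so the check asks what each reading of the rule would pass.

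**Inputs.** Shares of 55%, 30% and 15% (Compliance; Appendix II). Count rule of 12 sessions over 4 months (Compliance; Appendix I). Typical ranges of 8-20 individual, 4-10 family, 4-10 parent and 4-10 community sessions (Intervention). Pilot MDFT arm of 30 (Internal pilot study). Cut-offs of 80% and 60% (Appendix II).

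**1. Shares as joint minimums.** Let a, f and p be the adolescent, family and parent counts, with N = a + f + p. The rule is a ≥ 0.55N, f ≥ 0.30N and p ≥ 0.15N.
- 0.55 + 0.30 + 0.15 = 1.00, so there is no slack and all three must hold with equality. The mix must be exactly 11:6:3.
- Whole sessions allow this only when N is a multiple of 20. A search over N = 1 to 100 finds 20, 40, 60, 80 and 100.
- At N = 12 the required counts are 6.6, 3.6 and 1.8. A course of exactly 12 sessions, the protocol's other minimum, cannot pass.
- If any community session counts in the total, the three shares cannot reach 100% and nobody can pass.

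**2. Typical ranges.** There are 13 × 7 × 7 = 637 combinations before community sessions. The smallest total is 8 + 4 + 4 = 16.

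| Rule | Combinations that pass |
|---|---|
| At least 12 sessions in total | 637 of 637 |
| 55/30/15 as joint minimums | 0 of 637 |
| Each share within 1 point of 55/30/15 | 3 |
| Within 2 points | 12 |
| Within 3 points | 26 |
| Within 5 points | 75 (12%) |
| Within 10 points | 228 (36%) |

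With 4-10 community sessions counted in the total, there are 637 × 7 = 4,459 combinations and none meets the joint minimums. The bottom of the typical ranges (8/4/4) and the top (20/10/10) both give 50/25/25%. Each is 10 points from the stated parent share.

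**3. Does the mix measure dose?** A 6-session course of 3 adolescent, 2 family and 1 parent session is 50/33.3/16.7%. It lies within 5 points on every share at half the 12-session minimum. A 40-session course of 20/10/10 does not.

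**4. What the rating turns on.** 80% of 30 is 24 participants and 60% of 30 is 18, so red means fewer than 18 received the minimum dose.

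The tolerances are illustrative, since the protocol states none. The counts are possible mixes, not forecasts of participant percentages, because the protocol gives no delivered-session data.

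**The case against.** The strongest reply is that three shares adding to exactly 100% are naturally a planned mix, and the text never says that each is a floor. On that reading the two statements are compatible: 12 sessions split 7/3/2 is 58/25/17%, within 5 points throughout. The zero out of 637 also depends partly on the grid. A course of 11/6/3 meets the shares exactly but falls just outside it, with 3 parent sessions against a typical minimum of 4, and the ranges are only typical. The windows can be seen as nested within a therapy lasting 4-6 months. Session composition matters in a family therapy too, since a bare count would pass 12 adolescent-only sessions. Finally, this is one of 14 rows in Appendix II, with no stopping rule attached to a red rating on it.

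Much of this stands. The mix reading is the more natural one, the joint-minimum result is the extreme case, and composition is worth reporting. But the mix reading does not repair the item. Without a tolerance it gives no pass or fail, and with one it still passes a 6-session course. Nor does it help to read the first line as 55% of planned sessions: the other two lines do not say that, and the Activities section of Appendix I makes the length and intensity of treatment individual, so no amount is fixed. Tolerance and rounding could be left to an analysis plan. The choice between a ratio and a count cannot, because the protocol itself fixes the criterion and contradicts it.

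**Conclusion.** The point holds. As written, the minimum-dose item in Appendix II cannot measure dose, and its rating is either unattainable or indeterminate depending on the reading. Within the typical ranges, the share of session mixes that pass runs from 0% (joint minimums) through 12% and 36% (tolerances of 5 and 10 points) to 100% (12-session count). The same delivery records could fall below 18 of 30 on one reading and above 24 of 30 on another. How likely that is cannot be said without data on sessions delivered.

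The harm is confined to this one progression item and to the definition of minimum dose. The primary analysis is by intention to treat, and the CACE analysis names its 12-session threshold directly, so neither changes. It should be fixed before the pilot item is rated.

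**What to change.** State one count-based minimum dose with one time window, and use it in the Compliance section, Appendix I, the Appendix II dose item and the lower CACE threshold. The protocol's own 12 sessions over 4 months would serve. If the clinical team wants to ensure family and parent work, add minimum counts for those domains. Say whether community sessions count towards the total. Keep 55/30/15 only as a descriptive target mix with a stated tolerance, reported separately from dose.

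The cost is wording in those places, before the pilot dose item is rated. No new data are needed: according to the Compliance section, the MDFT clinical portal already records dose, duration and the domain targeted at each session.
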